11.3.6 Visit 8 (Week 10)

- Study drug compliance
- ITP Bleeding Score

- Adverse events/concomitant medications
- Vital signs
- Laboratory tests (hematology and serum chemistry)
- Pharmacokinetics (1 to 4 hours after study drug administration)
- Study drug dispensed (Period I)^{a)}
- a) The need of dispensing the study drug is decided, considering the number of tablets to be taken before the next visit.

11.3.7 Visit 9 (Week 12)

In principle, subjects should take the morning dose of the study drug 1 to 4 hours before blood sampling and then visit the study institution in the morning.

- QOL evaluation (SF-36)^{a)}
- Study drug compliance
- ITP Bleeding Score
- Adverse events/concomitant medications
- ECOG Performance Status
- Vital signs
- Laboratory tests (hematology, serum chemistry, and urinalysis)
- Pregnancy test (women of childbearing potential only)
- Pharmacokinetics (1 to 4 hours after study drug administration)
- Study drug dispensed (Period I)^{b)}
- a) The QOL evaluation (SF-36) is performed before other procedures and evaluations.
- b) The need of dispensing the study drug is decided, considering the number of tablets to be taken before the next visit.

11.3.8 Visit 10 (Week 14)

- Study drug compliance
- ITP Bleeding Score
- Adverse events/concomitant medications
- Vital signs
- Laboratory tests (hematology and serum chemistry)
- Pharmacokinetics (1 to 4 hours after study drug administration)
- Study drug dispensed (Period I)^{a)}
- a) The need of dispensing the study drug is decided, considering the number of tablets to be taken before the next visit.

11.3.9 Visit 11 (Week 16)

In principle, subjects should take the morning dose of the study drug 1 to 4 hours before blood sampling and then visit the study institution in the morning.

- Study drug compliance
- ITP Bleeding Score
- Adverse events/concomitant medications
- ECOG Performance Status
- Vital signs
- Laboratory tests (hematology, serum chemistry, and urinalysis)
- Pharmacokinetics (1 to 4 hours after study drug administration)
- Study drug dispensed (Period I)^{a)}
- a) The need of dispensing the study drug is decided, considering the number of tablets to be taken before the next visit.

11.3.10 Visit 12 (Week 18)

In principle, subjects should take the morning dose of the study drug 1 to 4 hours before blood sampling and then visit the study institution in the morning.

- Study drug compliance
- ITP Bleeding Score
- Adverse events/concomitant medications
- Vital signs
- Laboratory tests (hematology and serum chemistry)
- Pharmacokinetics (1 to 4 hours after study drug administration)
- Study drug dispensed (Period I)^{a)}
- a) The need of dispensing the study drug is decided, considering the number of tablets to be taken before the next visit.

11.3.11 Visit 13 (Week 20)

- Study drug compliance
- ITP Bleeding Score
- Adverse events/concomitant medications
- ECOG Performance Status
- Vital signs
- Laboratory tests (hematology, serum chemistry, and urinalysis)

- Pharmacokinetics (1 to 4 hours after study drug administration)
- Study drug dispensed (Period I)^{a)}
- a) The need of dispensing the study drug is decided, considering the number of tablets to be taken before the next visit.

11.3.12 Visit 14 (Week 22)

In principle, subjects should take the morning dose of the study drug 1 to 4 hours before blood sampling and then visit the study institution in the morning.

- Study drug compliance
- ITP Bleeding Score
- Adverse events/concomitant medications
- Vital signs
- Laboratory tests (hematology and serum chemistry)
- Pharmacokinetics (1 to 4 hours after study drug administration)
- Study drug dispensed (Period I)^{a)}
- a) The need of dispensing the study drug is decided, considering the number of tablets to be taken before the next visit.

11.3.13 Visit 15 (Week 24)

- QOL evaluation (SF-36)^{a)}
- Study drug compliance
- ITP Bleeding Score
- Adverse events/concomitant medications
- ECOG Performance Status
- 12-lead ECG^{b)}
- Vital signs
- Laboratory tests (hematology, serum chemistry, and urinalysis)
- Immunoglobulin test
- Pregnancy test (women of childbearing potential only)
- Pharmacokinetics (1 to 4 hours after study drug administration)
- Enrollment for Transition to Period II
- Study drug dispensed (Period II)
- a) The QOL evaluation (SF-36) is performed before other procedures and evaluations.
- b) In principle, the 12-lead ECG is taken before the vital signs, laboratory tests, immunoglobulin test, pregnancy test (women of childbearing potential only), and pharmacokinetics.

11.4 Period II (Subjects Who Completed Period I)

11.4.1 Visit 16 (Week 28)

- Study drug compliance
- ITP Bleeding Score
- Adverse events/concomitant medications
- ECOG Performance Status
- Vital signs
- Laboratory tests (hematology, serum chemistry, and urinalysis)
- Study drug dispensed (Period II)

11.4.2 Visit 17 (Week 32) and Visit 18 (Week 36)

- Study drug compliance
- ITP Bleeding Score
- Adverse events/concomitant medications
- ECOG Performance Status
- Vital signs
- Laboratory tests (hematology and serum chemistry)
- Study drug dispensed (Period II)

11.4.3 Visit 19 (Week 40)

- Study drug compliance
- ITP Bleeding Score
- Adverse events/concomitant medications
- ECOG Performance Status
- Vital signs
- Laboratory tests (hematology, serum chemistry, and urinalysis)
- Pregnancy test (women of childbearing potential only)
- Study drug dispensed (Period II)

11.4.4 Visit 20 (Week 44) and Visit 21 (Week 48)

- Study drug compliance
- ITP Bleeding Score
- Adverse events/concomitant medications
- ECOG Performance Status

- Vital signs
- Laboratory tests (hematology and serum chemistry)
- Study drug dispensed (Period II)

11.4.5 Visit 22 (Week 52)

- QOL evaluation (SF-36)^{a)}
- Study drug compliance
- ITP Bleeding Score
- Adverse events/concomitant medications
- ECOG Performance Status
- 12-lead ECG^{b)}
- Vital signs
- Laboratory tests (hematology, serum chemistry, and urinalysis)
- Immunoglobulin test
- Pregnancy test (women of childbearing potential only)
- Written informed consent (only for subjects who want to participate in the Non-dosing period and Period III)
- a) The QOL evaluation (SF-36) is performed before other procedures and evaluations.
- b) In principle, the 12-lead ECG is taken before vital signs, laboratory tests, immunoglobulin test, and pregnancy test (women of childbearing potential only).

11.5 Period II (Early Transition Subjects)

11.5.1 ET Visit 1 (ET Day 1)

If the subject withdraws from Period I and transition to Period II, in principle, the study procedures on ET Day 1 will be performed on the same day as the last visit in Period I. When the study procedures on ET Day 1 are performed on the same day as the last visit for Period I, the procedures overlapping on ET Day 1 with the last visit of Period I may be omitted when the procedures on ET Day 1 are performed. If the procedures on ET Day 1 cannot be performed on the same day as the last visit of Period I, all procedures on ET Day 1 must be performed within 1 week from the last visit of Period I. All procedures on ET Day 1 should be performed on the same day.

- QOL evaluation (SF-36)^{a)}
- Study drug compliance
- ITP Bleeding Score
- Adverse events/concomitant medications
- ECOG Performance Status
- 12-lead ECG^{b)}

- Vital signs
- Laboratory tests (hematology, serum chemistry, and urinalysis)
- Immunoglobulin test
- Pregnancy test (women of childbearing potential only)
- Inclusion/exclusion criteria
- Enrollment for Transition to Period II
- Study drug dispensed (Period II)
- a) The QOL evaluation (SF-36) is performed prior to other procedures and assessments on ET Day 1.
- b) In principle, the 12-lead ECG is taken before vital signs, laboratory tests, immunoglobulin test, and pregnancy test (women of childbearing potential only).

11.5.2 ET Visit 2 (ET Week 4)

- Study drug compliance
- ITP Bleeding Score
- Adverse events/concomitant medications
- ECOG Performance Status
- Vital signs
- Laboratory tests (hematology, serum chemistry, and urinalysis)
- Study drug dispensed (Period II)

11.5.3 ET Visit 3 (ET Week 8) and ET Visit 4 (ET Week 12)

- Study drug compliance
- ITP Bleeding Score
- Adverse events/concomitant medications
- ECOG Performance Status
- Vital signs
- Laboratory tests (hematology and serum chemistry)
- Study drug dispensed (Period II)

11.5.4 ET Visit 5 (ET Week 16)

- Study drug compliance
- ITP Bleeding Score
- Adverse events/concomitant medications
- ECOG Performance Status
- Vital signs

- Laboratory tests (hematology, serum chemistry, and urinalysis)
- Pregnancy test (women of childbearing potential only)
- Study drug dispensed (Period II)

11.5.5 ET Visit 6 (ET Week 20) and ET Visit 7 (ET Week 24)

- Study drug compliance
- ITP Bleeding Score
- Adverse events/concomitant medications
- ECOG Performance Status
- Vital signs
- Laboratory tests (hematology and serum chemistry)
- Study drug dispensed (Period II)

11.5.6 ET Visit 8 (ET Week 28)

- QOL evaluation (SF-36)^{a)}
- Study drug compliance
- ITP Bleeding Score
- Adverse events/concomitant medications
- ECOG Performance Status
- 12-lead ECG^{b)}
- Vital signs
- Laboratory tests (hematology, serum chemistry, and urinalysis)
- Immunoglobulin test
- Pregnancy test (women of childbearing potential only)
- Written informed consent (only for subjects who want to participate in the Non-dosing period and Period III)
- a) The QOL evaluation (SF-36) is performed before other procedures and evaluations.
- b) In principle, the 12-lead ECG is taken before vital signs, laboratory tests, immunoglobulin test, and pregnancy test (women of childbearing potential only).

11.6 Non-dosing Period

11.6.1 ND Visit 1 (ND Week 2)

The study procedures for ND Week 2 are not performed for subjects who skip the Non-dosing period and transition to Period III, or transition from the Non-dosing period to Period III before performing the study procedures for ND Week 2.

• QOL evaluation (SF-36)^{a)}

- ITP Bleeding Score
- Adverse events/concomitant medications
- ECOG Performance Status
- 12-lead ECG^{b)}
- Vital signs
- Laboratory tests (hematology, serum chemistry, and urinalysis)
- Immunoglobulin test
- Pregnancy test (women of childbearing potential only)
- a) The QOL evaluation (SF-36) is performed before other procedures and evaluations.
- b) In principle, the 12-lead ECG is taken before vital signs, laboratory tests, immunoglobulin test, and pregnancy test (women of childbearing potential only).

11.7 Period III

11.7.1 Period III Visit 1 (Period III Day 1)

The study procedures for Period III Day 1 are not performed for subjects who skip the Non-dosing period and transition to Period III. The study procedures for Period III Day 1 will be immediately performed irrespective of the allowance of visit for subjects who transition from the Non-dosing period to Period III before completing the Non-dosing period. When the study procedures on Period III Day 1 are performed on the same day as hose for ND Week 2, the procedures overlapping on Period III Day 1 with ND Week 2 may be omitted when the procedures on Period III Day 1 are performed.

- QOL evaluation (SF-36)^{a)}
- ITP Bleeding Score
- Adverse events/concomitant medications
- ECOG Performance Status
- 12-lead ECG^{b)}
- Vital signs
- Laboratory tests (hematology, serum chemistry, and urinalysis)
- Immunoglobulin test
- Pregnancy test (women of childbearing potential only)
- Study drug dispensed (Period III)
- a) The QOL evaluation (SF-36) is performed before other procedures and evaluations.
- b) In principle, the 12-lead ECG is taken before vital signs, laboratory tests, immunoglobulin test, and pregnancy test (women of childbearing potential only).

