- a) Subjects with platelet count of < 50000/µL at Week 52 or at ET Week 28 may skip the Non-dosing period and transition to Period III at the discretion of the investigator. The study procedures for Day 1 of Period III are immediately performed irrespective of the allowance of visit for subjects who transition from the Non-dosing period to Period III before completing the Non-dosing period.
- b) The tests on the Withdrawal Visit are not performed for subjects who withdraw from the Non-dosing period.
- c) The study procedures for ND Week 2 are not performed for subjects who skip the Non-dosing period and transition to Period III, or transition from the Non-dosing period to Period III before performing the study procedures for ND Week 2.
- d) When the study procedures on Day 1 of Period III are performed on the same day as those for ND Week 2, the procedures overlapping on Day 1 of Period III with ND Week 2 may be omitted when the procedures on Day 1 of Period III are performed. The study procedures for Day 1 of Period III are omitted for subjects who skip the Non-dosing period and transition to Period III.
- e) The tests at the end of the follow-up period are performed at Week 52 or 2 weeks after ET Week 28 for subjects who withdraw from the Non-dosing period before ND Week 2. The tests at the end of the follow-up period are not performed for subjects who withdraw from the Non-dosing period at ND Week 2 or later.
- f) Written informed consent is obtained from subjects who want to participate in the Non-dosing period and Period III.
- g) In principle, the 12-lead ECG is taken before vital signs, laboratory tests, immunoglobulin test, and pregnancy test (women of childbearing potential only).
- h) Pregnancy testing should be performed for all female subjects of childbearing potential no matter with or without contraception.
- i) SF-36 assessment is performed prior to other procedures and assessments.
- j) Only the use of ITP drugs is checked during Period III or later.

TABLE OF CONTENTS

History and Background of Study Plan	2 2
1.1 Idiopathic Thrombocytopenic Purpura	22
1.2 Treatment of ITP	22
1.3 Development History of R788	24
1.4 Summary of Expected Adverse Drug Reactions and Benefits	28
2. Title of Study and Study Phase	30
2.1 Title of Study	30
2.2 Study Phase	30
3. Objective	30
3.1 Primary Objective	30
3.2 Secondary Objectives	30
3.3 Exploratory Objective	30
4. Endpoints	30
4.1 Efficacy Endpoints	30
4.2 Safety Endpoints	32

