8.4 Transition to Non-dosing Period

Subjects who provide written informed consent to participate in the Non-dosing period and Period III transition to the Non-dosing period. However, subjects with platelet count of $<50000/\mu L$ at Week 52 or at ET Week 28 may skip the Non-dosing period and transition to Period III at the discretion of the investigator.

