morning on the day of the visit start the study drug for Period II from the evening of the same day). The dose and administration at the start of the study drug for Period II is as follows.

- If the last dose and administration in Period I is 100 mg *bid* or 150 mg *bid*, study drug in Period II is initiated with 100 mg *bid*.
- If the last dose and administration in Period I is 100 mg qd or 150 mg qd, study drug in Period II is initiated with the last dose and administration in Period I.

The dose should be adjusted during Period II in accordance with "8.6.2 Dose adjustment." Morning and evening doses should be at least 8 hours apart and should be taken at approximately the same time each day, with or without food during the Period II.

4) Non-dosing period

[figure not shown]
No study drug is administered.

5) Period III

The study drug is administered orally until market authorization of R788 in Japan. The study drug for Period III is initiated with the last dose and administration of study drug in Period II and is started after the visit on Day 1 of Period III. The dose should be adjusted during Period III in accordance with "8.6.2 Dose adjustment." Morning and evening doses should be at least 8 hours apart and should be taken at approximately the same time each day, with or without food during the Period III.

6) Follow-up period

No study drug is administered.

This does not apply to cases when dose is adjusted according to "8.6.2.2 Dose adjustment due to adverse events" or "8.6.2.3 Dose adjustment due to excessive elevation of platelet count."

a) The dose of 100 mg of the study drug is administered at study institutions and this must be the only administration of the study drug on Day 1, irrespective of the time of administration.

Figure 8.6.1-1 Dose and Administration Method for Subjects Who Complete Period I

Period I (double blind) 24 weeks		Period II (open label) 28 weeks		Non-dosing period Up to 4 weeks	Period III (Open label) Until market authorization	
Day 1 or later Week 4 or later ET D		Day 1	ET Week 4 or later		Day 1 or later in Period III	
	150 mg bid elet < 50000/µL tudy drug is well tolerated 100 mg bid	150 mg bid	100 mg bid	Platelet < 50000/µI and study drug is w tolerated		The study drug is initiated with the last dose and administration in Period II.

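### Subjects who skip the Non-dosing period have no study drug dispensing listed from Week 52 or ET Week 28 until Period III Week 8, although the protocol intends them to stay on drug

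*Protocol*

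**What the plan says.** Protocol 8.4 sends consenting subjects into the Non-dosing period, but those with platelets below 50000/µL at Week 52 or ET Week 28 "may skip the Non-dosing period and transition to Period III at the discretion of the investigator". For Period III, 8.6.1 states: "The study drug is administered orally until market authorization of R788 in Japan". It carries the last Period II dose forward and says that the Period III drug "is started after the visit on Day 1 of Period III".

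Section 11.7.1, which covers Period III Day 1, then states: "The study procedures for Period III Day 1 are not performed for subjects who skip the Non-dosing period and transition to Period III". Footnote d) of the Study Schedule for Non-dosing Period and Period III repeats the rule: "The study procedures for Day 1 of Period III are omitted for subjects who skip the Non-dosing period and transition to Period III". Neither makes an exception for dispensing, which is the last item in the 11.7.1 list.

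The next-nearest visit is removed as well. Section 11.6.1 says: "The study procedures for ND Week 2 are not performed for subjects who skip the Non-dosing period and transition to Period III". That visit has no dispensing for anyone.

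For a different overlap, Day 1 falling on the same day as ND Week 2, 11.7.1 uses a narrower rule: "the procedures overlapping on Period III Day 1 with ND Week 2 may be omitted".

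**The concern.** The only reason to skip the Non-dosing period is to avoid taking a subject with low platelets off drug. The visit lists do not carry that through. A site that follows them finds no instruction to hand out drug at Week 52 or ET Week 28, and is told not to carry out the Day 1 list that contains the instruction. The next entry is Period III Week 8. Section 8.6.1 does not settle the matter, because it ties the start of Period III drug to a Day 1 visit whose procedures these subjects do not have.

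At stake is continuity of treatment in subjects below 50000/µL. Read literally, the schedule could impose an interruption longer than the four-week maximum of the Non-dosing period that the investigator had decided against. Period III exposure and platelet summaries for these subjects would also be affected, but those are descriptive.

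**Working it through.** The plan gives no figure for this point, so there is none to reproduce. The check traces the dispensing entries, compares the lists and then does the supply arithmetic.

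**1. Dispensing entries for a subject who skips the Non-dosing period**

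| Visit | Dispensing listed? | Source |
|---|---|---|
| Week 48 or ET Week 24 | Yes (Period II drug) | 11.4.4, 11.5.5 |
| Week 52 or ET Week 28 | No | 11.4.5, 11.5.6 |
| ND Week 2 | Visit removed; no dispensing in its list | 11.6.1 |
| Period III Day 1 | Listed, but all procedures removed | 11.7.1, footnote d) |
| Period III Week 8 | Yes (Period III drug) | 11.7.2 |

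The schedule tables agree with the text of section 11: the Period II dispensing marks end at Week 48 and ET Week 24. The gap is therefore not an effect of how the tables were extracted.

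**2. Overlap of the lists**

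Section 11.7.1 has 10 items: SF-36, ITP Bleeding Score, adverse events and concomitant medications, ECOG status, ECG, vital signs, laboratory tests, immunoglobulins, pregnancy test and dispensing. Sections 11.4.5 and 11.5.6 each have 11 items, which include the first nine of these (plus compliance and consent). Section 11.6.1 has exactly those nine.

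- Items not already covered at Week 52 or ET Week 28: 10 − 9 = 1, which is dispensing.
- Applied to these subjects, the overlap rule used for ND Week 2 would keep that one item. The blanket omission removes it.

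**3. Length of the gap**

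Assume that Period III Day 1 is the Week 52 or ET Week 28 day for these subjects. This follows from 8.2, where the Non-dosing period runs from that visit to Period III Day 1, if its length is zero. The protocol does not say so for them explicitly.

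- Period III Week 8 = 8 × 7 = 56 days after Day 1. With the ±14-day window: 56 − 14 = 42 to 56 + 14 = 70 days.

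**4. Drug needed to cover it**

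- Twice daily (2 tablets/day): 2 × 56 = 112 tablets; range 2 × 42 = 84 to 2 × 70 = 140.
- Once daily (1 tablet/day, possible after dose reduction): 56 tablets; range 42 to 70.

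**5. What leftover Period II drug might cover**

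Bottles hold 60 tablets (7.2). The number of bottles dispensed per visit is not given. Assume one or two bottles at Week 48 or ET Week 24, a nominal 28 days to the next visit, and that leftover Period II stock may be used in Period III, which the documents do not address.

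| Dose, bottles | Tablets left | Days covered | Days uncovered (of 42 to 70) |
|---|---|---|---|
| bid, 1 | 60 − 56 = 4 | 2 | 40 to 68 |
| bid, 2 | 120 − 56 = 64 | 32 | 10 to 38 |
| qd, 1 | 60 − 28 = 32 | 32 | 10 to 38 |
| qd, 2 | 120 − 28 = 92 | 92 | 0 |

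The visit windows (Week 48: days 330 to 344; Week 52: days 358 to 372) allow an interval of 358 − 344 = 14 to 372 − 330 = 42 days, so the leftover could be larger or smaller than shown. For bid with one bottle it ranges from 60 − 28 = 32 tablets (16 days) down to none.

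**The case against.** The strongest reply is that 8.6.1 already governs. It places these subjects on drug in Period III at a stated dose, nothing tells a site to withhold drug, and a site told to give drug must supply it. On this view only a bullet is missing. One can add that section 10 describes study procedures as investigations, observations, tests and evaluations and contains no dispensing item, so in a translated document the omission may be meant for assessments only. Drug handling also follows a separate written procedure (7.4) that is not in the documents.

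Part of this stands. The gap is very probably unintended, sites would probably dispense, and the unseen procedure might cover the case. The supply scenarios rest on an assumed bottle count and run from no uncovered days to 68, so they bound the problem rather than estimate it. The number of such subjects is unknown, within a planned total of 24.

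The narrower reading of procedures does not hold, because dispensing is itself listed among the Day 1 procedures in 11.7.1. Nor does 8.6.1 remove the conflict: it confirms that drug is intended, but starts it after the visit whose list is struck out. The protocol's other boundaries show what was meant. Week 24 lists Period II dispensing, and ET Day 1 on the same day as the last Period I visit drops only overlapping items. The Period I note that dispensing depends on the tablets needed before the next visit is not carried into the later schedules.

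**Conclusion.** The concern holds. As written, 11.7.1 and footnote d) remove the only dispensing entry that would supply these subjects between Week 52 or ET Week 28 and Period III Week 8, against the intent of 8.4 and 8.6.1. The listed gap is nominally 56 days (42 to 70), taking their Period III Day 1 as the Week 52 or ET Week 28 day. How many of those days would be without tablets cannot be determined from the documents.

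This is a drafting conflict that bears on continuity of treatment in low-platelet subjects. It does not touch the primary analysis or any inferential comparison. It is worth correcting because the literal instruction is wrong and the correction is small.

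**What to change.** In 11.7.1 and footnote d), limit the omission for these subjects to procedures that overlap with Week 52 or ET Week 28, using the approach already taken for ND Week 2. Dispensing then remains. Alternatively, add Period III dispensing, for these subjects only, to 11.4.5, 11.5.6 and the schedules.

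In 8.6.1, state that their Period III drug starts after the Week 52 or ET Week 28 visit. As an optional clarification, SAP 5.9 (Evaluation in Period III) could say that this visit is their Period III Day 1.

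The cost is one sentence in 11.7.1 and in footnote d), and one in 8.6.1. No visit or test is added; the only procedure kept is handing over the drug.
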